NDC	00405495601	SULFASALAZINE 500MG TABLET
NDC	00405495602	SULFASALAZINE 500MG TABLET
NDC	43353049553	SULFASALAZINE 500MG TABLET
NDC	43353049570	SULFASALAZINE 500MG TABLET
NDC	43353049580	SULFASALAZINE 500MG TABLET
NDC	00440842091	SULFASALAZINE 500MG TABLET
NDC	49727004204	SULFASALAZINE 500MG TABLET
NDC	49999098100	SULFASALAZINE 500MG TABLET
NDC	51382010701	SULFASALAZINE 500MG TABLET
NDC	51382010705	SULFASALAZINE 500MG TABLET
NDC	52544079601	SULFASALAZINE 500MG TABLET
NDC	52544079605	SULFASALAZINE 500MG TABLET
NDC	52544079610	SULFASALAZINE 500MG TABLET
NDC	53002029700	SULFASALAZINE 500MG TABLET
NDC	53489014701	SULFASALAZINE 500MG TABLET
NDC	53489014705	SULFASALAZINE 500MG TABLET
NDC	53489014710	SULFASALAZINE 500MG TABLET
NDC	00536461701	SULFASALAZINE 500MG TABLET
NDC	00536461705	SULFASALAZINE 500MG TABLET
NDC	00536461710	SULFASALAZINE 500MG TABLET

Code Type	Code	Description
NDC	00005396031	SULFASALAZINE 500MG TABLET
NDC	54569031301	SULFASALAZINE 500MG TABLET
NDC	54569031303	SULFASALAZINE 500MG TABLET
NDC	54868113800	SULFASALAZINE 500MG TABLET
NDC	54868113801	SULFASALAZINE 500MG TABLET
NDC	54868113803	SULFASALAZINE 500MG TABLET
NDC	54868113804	SULFASALAZINE 500MG TABLET
NDC	54868113805	SULFASALAZINE 500MG TABLET
NDC	54868113806	SULFASALAZINE 500MG TABLET
NDC	55289017610	SULFASALAZINE 500MG TABLET
NDC	55289017640	SULFASALAZINE 500MG TABLET
NDC	56126030611	SULFASALAZINE 500MG TABLET
NDC	58016007400	SULFASALAZINE 500MG TABLET
NDC	58016007430	SULFASALAZINE 500MG TABLET
NDC	58016007460	SULFASALAZINE 500MG TABLET
NDC	58016007490	SULFASALAZINE 500MG TABLET
NDC	00591079601	SULFASALAZINE 500MG TABLET
NDC	00591079605	SULFASALAZINE 500MG TABLET
NDC	00591079610	SULFASALAZINE 500MG TABLET
NDC	59762500001	SULFASALAZINE 500MG TABLET
NDC	59762500002	SULFASALAZINE 500MG TABLET
NDC	60346081240	SULFASALAZINE 500MG TABLET
NDC	60346081294	SULFASALAZINE 500MG TABLET
NDC	00603580221	SULFASALAZINE 500MG TABLET
NDC	00603580228	SULFASALAZINE 500MG TABLET
NDC	61392014730	SULFASALAZINE 500MG TABLET
NDC	61392014731	SULFASALAZINE 500MG TABLET
NDC	61392014732	SULFASALAZINE 500MG TABLET
NDC	61392014739	SULFASALAZINE 500MG TABLET
NDC	61392014745	SULFASALAZINE 500MG TABLET
NDC	61392014751	SULFASALAZINE 500MG TABLET
NDC	61392014754	SULFASALAZINE 500MG TABLET
NDC	61392014760	SULFASALAZINE 500MG TABLET
NDC	61392014790	SULFASALAZINE 500MG TABLET
NDC	61392014791	SULFASALAZINE 500MG TABLET
NDC	00615152253	SULFASALAZINE 500MG TABLET
NDC	00615152263	SULFASALAZINE 500MG TABLET
NDC	00615152265	SULFASALAZINE 500MG TABLET

PFIZER CONFIDENTIAL

CT24-WI-GL02-RF02 4.0 Non-Interventional Study Protocol Template For Secondary Data Collection Study

01-Jun-2022

Page 94 of 96

Code Type	Code	Description
NDC	00659010605	SULFASALAZINE 500MG TABLET
NDC	00677048301	SULFASALAZINE 500MG TABLET
NDC	00677048305	SULFASALAZINE 500MG TABLET
NDC	68258908601	SULFASALAZINE 500MG TABLET
NDC	00814723028	SULFASALAZINE 500MG TABLET
NDC	00839609806	SULFASALAZINE 500MG TABLET
NDC	00839609812	SULFASALAZINE 500MG TABLET
NDC	00904115240	SULFASALAZINE 500MG TABLET
NDC	00904115260	SULFASALAZINE 500MG TABLET
NDC	00254590528	SULFASALAZINE 500MG TABLET DR
NDC	59762010401	SULFASALAZINE 500MG TABLET DR
NDC	59762010402	SULFASALAZINE 500MG TABLET DR
NDC	59762010405	SULFASALAZINE DR 500 MG TABLET DR
NDC	59762010406	SULFASALAZINE DR 500 MG TABLET DR
NDC	54868113900	SULFASALAZINE EC 500MG TABLET DR
NDC	38779017604	SULFASALAZINE POWDER
NDC	38779017605	SULFASALAZINE POWDER
NDC	38779017608	SULFASALAZINE POWDER
NDC	38779017609	SULFASALAZINE POWDER
NDC	38779017610	SULFASALAZINE POWDER
NDC	38779017625	SULFASALAZINE POWDER
NDC	38779017644	SULFASALAZINE POWDER
NDC	49452752301	SULFASALAZINE POWDER
NDC	49452752302	SULFASALAZINE POWDER
NDC	51552104405	SULFASALAZINE POWDER
NDC	51927104500	SULFASALAZINE POWDER
NDC	62991270401	SULFASALAZINE POWDER
NDC	62991270403	SULFASALAZINE POWDER
NDC	62991270404	SULFASALAZINE POWDER
NDC	10544028830	SULFAZINE 500 MG TABLET
NDC	67544094370	SULFAZINE 500 MG TABLET
NDC	67544094380	SULFAZINE 500 MG TABLET
NDC	00603580104	SULFAZINE 500MG TABLET
NDC	00603580121	SULFAZINE 500MG TABLET
NDC	00603580128	SULFAZINE 500MG TABLET
NDC	00603580132	SULFAZINE 500MG TABLET
NDC	00603580321	SULFAZINE EC 500MG TABLET DR
NDC	00603580325	SULFAZINE EC 500MG TABLET DR

PFIZER CONFIDENTIAL

Code Type	Code	Description
NDC	51285036801	TREXALL 10MG TABLET
NDC	00555092901	TREXALL 10MG TABLET
NDC	51285036901	TREXALL 15MG TABLET
NDC	00555094501	TREXALL 15MG TABLET
NDC	51285036601	TREXALL 5MG TABLET
NDC	00555092701	TREXALL 5MG TABLET
NDC	51285036701	TREXALL 7.5MG TABLET
NDC	00555092801	TREXALL 7.5MG TABLET
NDC	52652200101	XATMEP 2.5 MG/ML SOLUTION
NDC	52652200106	XATMEP 2.5 MG/ML SOLUTION

Emergency room visit with RA as primary diagnosis

Emergency room visits associated with a diagnosis of RA (ICD-10 codes: M05* and M06*, except M06.1, M06.4) will be identified based on the presence of evaluation and management codes associated with emergency department visits and place of service codes.

Hospitalization with RA as primary diagnosis

Hospitalizations associated with a diagnosis of RA (ICD-10 code: M05* and M06*, except M06.1, M06.4) will be identified based on revenue codes, place of service codes, and provider specialty.

Document Approval Record

Document Name: A3921427_PROTOCOL- XELJANZ SHINGRIZ PASS_V2.1_05OCT2023

Document Title: A3921427_PROTOCOL- XELJANZ SHINGRIZ PASS_V2.1_05OCT2023

Signed By:	Date(GMT)	Signing Capacity
[name]	31-Oct-2023 15:47:51	EUQPPV Approval
[name]	31-Oct-2023 16:43:15	Manager Approval

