9.3.5.2. Secondary Outcome (Safety)

The secondary outcome for this study is disease flare: UC flare within the UC cohorts and RA flare within the RA cohorts.

For the UC cohorts, the secondary outcome will be defined by an algorithm based on the claims-based indicator of UC flare in the 90 days following the cohort entry date. Based on published literature,^{18,19} the claims-based composite algorithm of UC flare will include a combination of the following components:

- Change in UC therapy (ie, new start or switch);
 - Corticosteroids (oral, rectal, or injection);
 - 5-aminosalicylates (oral or rectal);
 - Immunosuppressants (ie, azathioprine, 6-mercaptopurine, cyclosporine, tacrolimus);
- Emergency room visit with UC as primary diagnosis;

- Hospitalization with UC as primary diagnosis;
- UC-related surgery (ie, colectomy, proctocolectomy).

For the RA cohorts, the secondary outcome will be defined by an algorithm based on the occurrence of a claims-based indicator of RA flare in the 90 days following cohort entry date. Based on published literature,^{20,21,22,23} claims-based composite algorithm of RA flare will include a combination of the following components:

- Change in RA therapy (eg, new start or switch from monotherapy to combination therapy);
 - Corticosteroids (oral or injection): initiation of, or change in, treatment with a short-acting oral glucocorticoid (eg, methylprednisolone 6-day dosing pack) or any parenteral glucocorticoid injection, excluding corticosteroids administered the same day as infusions for RA therapy;
 - Conventional synthetic disease-modifying antirheumatic drugs (csDMARDs) (ie, methotrexate, sulfasalazine, hydroxychloroquine, leflunomide);
- Emergency room visit with RA as primary diagnosis;
- Hospitalization with RA as primary diagnosis.

The claims-based indicators of disease flare will be identified based on drug (NDC and American Hospital Formulary Service [AHFS]), procedure (Healthcare Common Procedure Coding System [HCPCS], CPT[®], and International Classification of Diseases, 10th Revision, Procedure Coding System [ICD-10-PCS]), and diagnosis (ICD-10) codes. The specific codes that will be utilized to identify UC and RA disease flares are provided in [Annex 3](#).

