9.4.1. Optum Research Database

The ORD is a proprietary research database that contains the eligibility data, medical claims, and pharmacy claims from a large, commercial health plan affiliated with Optum. The individuals covered by this health plan are geographically diverse across the United States and comprise approximately 3% to 4% of the US population. As early as 1993, medical and pharmacy claims data are available for 65 million individuals with both medical and pharmacy benefit coverage. For 2021, data are available for approximately 12.6 million individuals with medical and pharmacy coverage.

Optum research activities utilize de-identified data from the ORD. Patient-identifiable information can only be accessed following approval of the study protocol by an appropriate institutional review board and privacy board. All data access conforms to applicable Health Insurance Portability and Accountability Act policies.

Accessible information from the ORD includes demographics, pharmacy use, and all medical and facility claims, which provide data on services, procedures, and their accompanying diagnoses.

The coding of medical claims conforms to insurance industry standards including:

- Use of designated claims forms (eg, physicians use the Health Care Financing Agency-1500 format and hospitals use the UB-04 or UB-92 format);
- International Classification of Diseases, 9th Revision codes;
- ICD-10 codes;
- CPT[®] codes³;
- HCPCS codes;
- Cost information;
- De-identified patient and provider codes.

³ CPT copyright 2022 American Medical Association. All rights reserved.

Claims for pharmacy services are typically submitted electronically by the pharmacy at the time prescriptions are filled. Pharmacy claims data allowing for longitudinal tracking of medication refill patterns and changes in medications include:

- NDC;
- Drug name;
- Dosage form;
- Drug strength;
- Fill date;
- Days of supply;
- Cost information;
- De-identified patient and prescriber codes.

An important advantage of the ORD is the large number of patients that can be studied because the data are routinely collected and maintained in computerized data files. The completeness of the data allows investigators to link any number of patient, physician, and treatment attributes, while maintaining the de-identified nature of the data. The database also captures a longitudinal record of medical services, irrespective of treatment site.

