As patients that have UC and RA may have different clinical characteristics compared to patients that have only one of the two diseases, the number of patients that have both diagnoses will be quantified. Additionally, a sensitivity analysis will be conducted in which the association between RZV exposure and the primary and secondary outcomes is assessed after excluding patients with both UC and RA from the exposure cohorts.

To assess the effect of prior Zostavax vaccination on subsequent RZV effect, an analysis will be performed where the study population is restricted to patients with at least 5 years of enrollment prior to cohort entry. Within this subset, the analysis will be conducted separately among patients with and without Zostavax vaccination during this baseline 5-year period. The effect of prior Zostavax exposure will be informed by the extent to which the estimate of RZV effect differs according to strata of prior Zostavax exposure.

It is possible that the comparator cohorts could include patients previously vaccinated with RZV more than 365 days earlier. To address this potential exposure misclassification, a sensitivity analysis will be performed, for which the study population will be restricted to patients with enrollment that extends back to 20 October 2017 and who do not have any prior administration of RZV during that time. Finally, a sensitivity analysis will be conducted for HZ in which patients are stratified based on their amount of available follow-up time.

Misclassification of disease flares is possible when using claims-based algorithms (for example, patients may change therapy for reasons other than disease flares), leading to over- or under-estimation of the outcome; thus, alternative definitions will be explored and outlined in the SAP as sensitivity analyses. Specifically, sensitivity analysis will explore using a more conservative definition based on only UC-related surgeries or ER and hospitalizations with UC or RA as the primary diagnosis, as well as evaluating more expansive definitions inclusive of other medications of interest, such as biologics or other JAK inhibitor treatments.

Additional sensitivity analysis may be performed if needed.

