NDC	71052005801	TACROLIMUS 100 % POWDER
NDC	71052005802	TACROLIMUS 100 % POWDER
NDC	38779227200	TACROLIMUS 100% POWDER
NDC	38779227203	TACROLIMUS 100% POWDER
NDC	38779227204	TACROLIMUS 100% POWDER
NDC	38779227206	TACROLIMUS 100% POWDER
NDC	51552112801	TACROLIMUS 100% POWDER
NDC	51552112804	TACROLIMUS 100% POWDER
NDC	51552112805	TACROLIMUS 100% POWDER
NDC	51552112806	TACROLIMUS 100% POWDER
NDC	51927355700	TACROLIMUS 100% POWDER
NDC	16714010001	TACROLIMUS 5 MG CAPSULE
NDC	16729004301	TACROLIMUS 5 MG CAPSULE
NDC	00378204701	TACROLIMUS 5 MG CAPSULE
NDC	00378204705	TACROLIMUS 5 MG CAPSULE
NDC	42291075401	TACROLIMUS 5 MG CAPSULE

Code Type	Code	Description
NDC	50742020901	TACROLIMUS 5 MG CAPSULE
NDC	51079002801	TACROLIMUS 5 MG CAPSULE
NDC	51079002820	TACROLIMUS 5 MG CAPSULE
NDC	55111052701	TACROLIMUS 5 MG CAPSULE
NDC	00591335901	TACROLIMUS 5 MG CAPSULE
NDC	60429037901	TACROLIMUS 5 MG CAPSULE
NDC	62175038237	TACROLIMUS 5 MG CAPSULE
NDC	63629872601	TACROLIMUS 5 MG CAPSULE
NDC	64380072206	TACROLIMUS 5 MG CAPSULE
NDC	67877028001	TACROLIMUS 5 MG CAPSULE
NDC	68084045101	TACROLIMUS 5 MG CAPSULE
NDC	68084045111	TACROLIMUS 5 MG CAPSULE
NDC	68462068701	TACROLIMUS 5 MG CAPSULE
NDC	69452015520	TACROLIMUS 5 MG CAPSULE
NDC	70377001611	TACROLIMUS 5 MG CAPSULE
NDC	70748022101	TACROLIMUS 5 MG CAPSULE
NDC	00781930401	TACROLIMUS 5 MG CAPSULE
NDC	00904662461	TACROLIMUS 5 MG CAPSULE
NDC	00781210201	TACROLIMUS ANHYDROUS 0.5MG CAPSULE
NDC	00781210301	TACROLIMUS ANHYDROUS 1MG CAPSULE
NDC	00781210401	TACROLIMUS ANHYDROUS 5MG CAPSULE
NDC	63275995801	TACROLIMUS MICRONIZED 100% POWDER
NDC	63275995802	TACROLIMUS MICRONIZED 100% POWDER
NDC	63275995806	TACROLIMUS MICRONIZED 100% POWDER
NDC	63275995807	TACROLIMUS MICRONIZED 100% POWDER

Emergency room visit with UC as primary diagnosis

Emergency room visits associated with a diagnosis of UC (ICD-10 code: K51*) will be identified based on the presence of evaluation and management codes associated with emergency department visits and place of service codes.

Hospitalization with UC as primary diagnosis

Hospitalizations associated with a diagnosis of UC (ICD-10 code: K51*) will be identified based on revenue codes, place of service codes, and provider specialty.

UC-related surgery

Code Type	Code	Description
CPT [®]	44139	Mobilization (take-down) of splenic flexure performed in conjunction with partial colectomy (List separately in addition to primary procedure)
CPT	44140	Colectomy, partial; with anastomosis

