CPT	44141	Colectomy, partial; with skin level cecostomy or colostomy
CPT	44143	Colectomy, partial; with end colostomy and closure of distal segment (Hartmann type procedure)
CPT	44144	Colectomy, partial; with resection, with colostomy or ileostomy and creation of mucofistula
CPT	44145	Colectomy, partial; with coloproctostomy (low pelvic anastomosis)
CPT	44146	Colectomy, partial; with coloproctostomy (low pelvic anastomosis), with colostomy
CPT	44147	Colectomy, partial; abdominal and transanal approach
CPT	44150	Colectomy, total, abdominal, without proctectomy; with ileostomy or ileoproctostomy
CPT	44151	Colectomy, total, abdominal, without proctectomy; with continent ileostomy
CPT	44155	Colectomy, total, abdominal, with proctectomy; with ileostomy
CPT	44156	Colectomy, total, abdominal, with proctectomy; with continent ileostomy
CPT	44157	Colectomy, total, abdominal, with proctectomy; with ileoanal anastomosis, includes loop ileostomy, and rectal mucosectomy, when performed
CPT	44158	Colectomy, total, abdominal, with proctectomy; with ileoanal anastomosis, creation of ileal reservoir (S or J), includes loop ileostomy, and rectal mucosectomy, when performed
CPT	44160	Colectomy, partial, with removal of terminal ileum with ileocolostomy
CPT	44204	Laparoscopy, surgical; colectomy, partial, with anastomosis
CPT	44205	Laparoscopy, surgical; colectomy, partial, with removal of terminal ileum with ileocolostomy
CPT	44206	Laparoscopy, surgical; colectomy, partial, with end colostomy and closure of distal segment (Hartmann type procedure)
CPT	44207	Laparoscopy, surgical; colectomy, partial, with anastomosis, with coloproctostomy (low pelvic anastomosis)
CPT	44208	Laparoscopy, surgical; colectomy, partial, with anastomosis, with coloproctostomy (low pelvic anastomosis) with colostomy
CPT	44210	Laparoscopy, surgical; colectomy, total, abdominal, without proctectomy, with ileostomy or ileoproctostomy
CPT	44211	Laparoscopy, surgical; colectomy, total, abdominal, with proctectomy, with ileoanal anastomosis, creation of ileal reservoir (S or J), with loop ileostomy, includes rectal mucosectomy, when performed
CPT	44212	Laparoscopy, surgical; colectomy, total, abdominal, with proctectomy, with ileostomy
CPT	44213	Laparoscopy, surgical, mobilization (take-down) of splenic flexure performed in conjunction with partial colectomy (List separately in addition to primary procedure)

⁵ CPT copyright 2022 American Medical Association. All rights reserved.

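### Annex 3 defines UC-related surgery by procedure code alone, so a bowel operation for another disease is scored as a UC flare, even in the conservative definition

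*Protocol*

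**What the plan says.** Section 9.3.5.2 builds the UC flare outcome from therapy changes and three severe components. Two of these name the diagnosis: "Emergency room visit with UC as primary diagnosis" and "Hospitalization with UC as primary diagnosis". The third is UC-related surgery, explained only by type of operation (colectomy, proctocolectomy). The section refers the reader to Annex 3 for the specific codes, so the code list is fixed in the protocol and is not deferred to the SAP.

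In Annex 3 the headings for emergency room visits and admissions repeat the primary-diagnosis condition. The sentences beneath them are looser: "Emergency room visits associated with a diagnosis of UC (ICD-10 code: K51*) will be identified" and "Hospitalizations associated with a diagnosis of UC (ICD-10 code: K51*) will be identified based on revenue codes, place of service codes, and provider specialty". Under UC-related surgery there is no sentence at all, only a table of procedure codes. One row, for example, reads "Colectomy, partial, with removal of terminal ileum with ileocolostomy".

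Two other places use the surgery component. Exclusion 4 in Section 9.2.2 removes patients who had it in the 91 days before cohort entry. Section 9.7.4 plans "a more conservative definition based on only UC-related surgeries or ER and hospitalizations with UC or RA as the primary diagnosis".

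**The concern.** Nothing in Annex 3 makes a listed operation UC-related except its presence on the list, and most of the listed operations are not specific to UC. A patient enters the UC cohort on one K51* claim in any position within 365 days (Section 9.3.2). Section 9.3.6.3 lists malignancy and Crohn's disease as covariates, and Section 9.2.2 excludes neither. A patient whose colon is resected for one of those diseases can therefore be in the cohort, and the operation would be recorded as a UC flare.

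The severe components are meant to be the specific part of the composite. They make up the whole of the conservative definition, which is the plan's check on misclassification from therapy changes. A non-specific surgery list weakens that check. It also lets an operation unrelated to flare remove a patient through exclusion 4, which covers the primary 2-dose HZ analysis as well as the flare analysis.

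**Working it through.** The protocol states no figure that depends on this definition, so the check is a comparison of sections and a count of codes.

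**Diagnosis condition by component (UC):**

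| Component | 9.2.2, exclusion 4 | 9.3.5.2 | 9.7.4, conservative | Annex 3 |
|---|---|---|---|---|
| Emergency room visit | primary | primary | primary | primary in heading; not repeated in sentence |
| Hospitalization | primary | primary | primary | primary in heading; not repeated in sentence |
| Surgery | none beyond the label | none beyond the label | none beyond the label | none; code list only |

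**CPT codes in the surgery list:**
- Partial colectomy or its add-on: 44139, 44140, 44141, 44143 to 44147, 44160, 44204 to 44208, 44213. That is 1 + 1 + 1 + 5 + 1 + 5 + 1 = 15.
- Total colectomy, with or without proctectomy: 44150, 44151, 44155 to 44158, 44210 to 44212. That is 1 + 1 + 4 + 3 = 9.
- 45121, whose descriptor names congenital megacolon: 1.
- Total: 15 + 9 + 1 = 25.

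**ICD-10-PCS codes:**
- Excision: seven body parts (E, F, G, K, L, M, N) with five approaches each, plus 0DBLFZZ. That is 7 × 5 + 1 = 36. Seven of these, one per body part, are endoscopic through a natural or artificial opening (0DBE8ZZ and its counterparts).
- Resection: four for the large intestine (0DTE) and four for the rectum alone (0DTP), 8 in all.
- Total: 36 + 8 = 44.

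The list therefore holds 25 + 44 = 69 codes, none tied to K51*.

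**Direction of the effect.** Let s be the share of counted comparator events that are unrelated to flare, and let those events occur at the same rate in both arms. With a comparator rate r for counted events, the vaccinated rate is HR × (1 − s) × r + s × r, so

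HR observed = (1 − s) × HR + s.

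The documents give neither s nor HR, so both are assumptions. With a true HR of 1.5, s = 0 returns 1.50 and s = 0.2 returns 0.8 × 1.5 + 0.2 = 1.40. For surgery alone, s is probably toward or below the low end of that range. In the main composite, therapy changes add further events, so the share due to misattributed surgery is smaller there than among severe events.

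**The case against.** The label itself says UC-related, and a programmer might read a diagnosis condition into it. The patients have a recent UC claim and are current tofacitinib users at entry, the flare window is only 90 days, and Section 9.9 acknowledges flare misclassification. These points limit the size of the problem. They do not remove it: the label is never turned into a claims rule, Annex 3 supplies the codes without one, and the example in Section 9.9 is medication change, not surgery. The RA flare definition has no surgery component and is unaffected.

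A reader might also infer from the Annex 3 sentences that emergency room visits and admissions need only carry K51* in some position. The documents do not support that. The sentences stand under headings that require UC as primary diagnosis, and Sections 9.2.2, 9.3.5.2 and 9.7.4 repeat the condition. Where the protocol accepts any diagnosis position, as for cohort eligibility in Section 9.3.2, it says so. The same applies to the RA sentence, "Hospitalizations associated with a diagnosis of RA (ICD-10 code: M05* and M06*, except M06.1, M06.4".

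A further inference is that an inpatient consultant who lists K51* first would turn an unrelated stay into a UC flare. Section 9.4.1 says only that "physicians use the Health Care Financing Agency-1500 format and hospitals use the UB-04 or UB-92 format". Nothing in the protocol says that a professional claim sets the primary diagnosis of a stay, and assembling a stay from its claims is detail commonly left to the SAP. Nor do the documents support a false signal from post-vaccination visits that list UC as a comorbidity, because a secondary code does not meet the primary-diagnosis condition.

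**Conclusion.** The point holds for surgery. Followed as written, the code list counts operations for other diseases as UC flares in both the main and the conservative definition, and it can exclude patients who had no flare. If these operations are equally common in the two arms, the flare hazard ratio moves toward 1, which is the unfavourable direction for a safety objective.

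The protocol gives no surgery counts or event split, so the size cannot be computed; it is probably small. The conclusion rests on three assumptions: each listed component is sufficient on its own for a flare, exclusion 4 uses the same surgery list (the protocol gives no other), and some listed operations in UC-cohort patients are done for other diseases. The change is worth making because it is cheap, but the point does not undermine the study.

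For emergency room visits and admissions, only an editorial mismatch remains between the Annex 3 headings and the sentences under them.

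**What to change.** 1. In Annex 3, count a listed operation only if K51* is the primary diagnosis on the surgical claim or stay. This matches the rule for the other severe components.
2. Remove or justify CPT 45121 and the seven endoscopic excision codes. The four codes for resection of the rectum alone deserve the same review.
3. State that the same rule applies to exclusion 4 in Section 9.2.2 and to the conservative definition in Section 9.7.4.
4. As editorial alignment only, repeat the word primary in the Annex 3 emergency room and hospitalization sentences for UC and RA.

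The cost is a few lines of annex text and programming, using diagnosis fields already in the claims. The downside is that a few true UC operations whose claim lists a complication first will be lost, with a slightly lower event count.
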